Hypothesis: Polyfunctional flow cytometric analysis will elucidate differential T cell and invariant NKT cell activation responses involved in the expression of peanut allergy in subjects prior to and after desensitization through detection of the following.

- a. Cytokines: IL-2, IL-4, IL-10, IFN γ , IL-13, IL-12, IL-5, IL-17, CD152
- b. Transcription factors: GATA-3, T-bet, STAT-6, STAT-4
- c. Memory Cell Surface Markers: CCR-7, CD45RO
- d. Activation Surface Markers: CD40L, CD25, CD69, CD30, IL12RB2
- e. T regulatory markers: CD127, CD39, CD73, GARP, Foxp3

A TH2 CD4⁺ T cell response and invariant NKT cell response, characterized by the intracellular expression of GATA3, IL-4 and IL-13 will characterize the responses in peanut allergic subjects prior to desensitization and, afterwards, peanut allergic patients will have a CD4⁺ T cell response with a higher t-bet, IL-5, IL-10, INF γ , IL-17 and FOXP3 expression and an increased regulatory and memory T cell phenotype.

The clarification of the roles of TH1, TH2, TH17, iNKT and T regulatory peanut specific antigen responses in peanut allergic disease before and after desensitization will help define immune mechanisms involved in the expression of allergic inflammation in vivo in peanut allergy. T cell epitopes will be determined through tetramer technology on saved samples, requiring HLA typing of all participants through buccal mucosal scraping analysis. Gene profiling will be performed on samples as well. Furthermore, basophil histamine release assays will also serve as an additional measure to discriminate between individuals who have developed tolerance and those that have not. This research plan is likely to provide a framework for further investigation of responses underlying the development of IgE compared to non-IgE mediated food allergic disease.

SIGNIFICANCE:

Th1/Th2/Treg response

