9. MEASUREMENT OF EFFECT

9.1. Response Review:

The Data Safety Monitoring Committee will review the responses to the primary and secondary objectives every 6 months during the trial.

9.2. Response Criteria:

9.2.1. The primary objective will be measured by recording the daily symptoms experienced by the subjects and the number of subjects with no clinical symptoms during 6 g peanut flour challenge at time 50 weeks compared to time 0 weeks. The change in tolerated dose will be assessed between baseline and one year. The proportion of patients who tolerate 6 g of peanut flour will be compared at baseline and at the one year point using McNemar's test for matched pair data. The proportion of subjects will be estimated with exact binomial confidence intervals.

9.2.2. For the first secondary objective, flow cytometric analysis of T, NKT cells, and basophils will be performed through the measurement of the percent of cells producing a

cytokine as well as measuring surface and intracellular markers expressed upon activation and the significance of changes from time 0 to 1 year will be assessed as described below by using a paired t-test of the log-transformed data. Baseline measures of cell activation will be summarized by means with standard deviation. Normality will be assessed by quantile-quantile plots, and non-normality will be addressed by data transformations. A general linear mixed model will be used to estimate the effect of the therapeutic procedure over time. The model will include a fixed effect for time (discrete), and the matrix of correlated error terms will assume a first-order autoregressive structure. Alternative correlation structures such as the unstructured and compound symmetry will be considered. Correlation structures will be assessed by Akaike's Information Criteria. The likelihood ratio test will be used to test for overall significance of the model. P-values will be adjusted using the Holm's step down Bonferonni correction for multiple comparisons. Activation responses that are significant at the 0.05 level after adjustment will be further assessed. Pairwise comparisons between discrete time points will be tested for significant differences, and p-values will be adjusted using the Bonferonni correction. Statistical significance of the adjusted p-values will be assessed at the 0.05 level.

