Spearman rank correlations will be estimated for all pairwise comparisons between activation responses. P-values for testing for significant correlations will be adjusted using Bonferonni's correction for multiple comparisons. Partial correlation coefficients will also be estimated for all activation responses adjusting for subject-level effects across all time points.

- 9.2.3. The second secondary objective will be assessed by recording the number of episodes of prior viral infection symptoms experienced after symptomatic daily peanut dosing. This number will be compared to the episodes of symptomatic daily peanut dosing with no prior viral infection symptoms. The proportion of subjects will be estimated with exact binomial confidence intervals. This analysis will also be used to determine the proportion of symptomatic daily doses with preceding symptoms of viral infection compared to non-viral associated symptomatic daily doses.
- 9.2.4. The third secondary objective will be assessed by the comparison of amount of peanut protein tolerated at the 24 month food challenge to the 25 month food challenge using McNemar's test for matched pair data.

[figure not shown]

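### Section 9.2.2 uses Holm for the overall marker tests but names Bonferroni for the time contrasts and marker correlations; naming Holm for all three is a free improvement whose size depends on unstated assumptions

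*Combined protocol and SAP*

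**What the plan says.** All three adjustments are in section 9.2.2 (Response Criteria, first secondary objective).

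- **Overall test per marker** (likelihood ratio test from the mixed model): "P-values will be adjusted using the Holm's step down Bonferonni correction for multiple comparisons". Only markers that remain significant at 0.05 go on to further testing.
- **Time contrasts**, later in the same paragraph: "Pairwise comparisons between discrete time points will be tested for significant differences, and p-values will be adjusted using the Bonferonni correction". The paragraph then adds: "Statistical significance of the adjusted p-values will be assessed at the 0.05 level".
- **Marker correlations**, in the next paragraph: "Spearman rank correlations will be estimated for all pairwise comparisons between activation responses", followed by "P-values for testing for significant correlations will be adjusted using Bonferonni's correction for multiple comparisons".

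The section gives no reason for changing the rule. It plans no simultaneous confidence intervals for the contrasts or correlations, which would be the usual reason to keep single-step Bonferroni. It does not state how many tests each family contains.

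**The concern.** Single-step Bonferroni compares every p-value in a family of m with 0.05/m. Holm compares the smallest with 0.05/m, the next with 0.05/(m − 1), and so on until one fails. Both hold the familywise error at 0.05 whatever the dependence between tests. Every Bonferroni rejection is also a Holm rejection, and the converse is not true.

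The plan already relies on Holm one step earlier, so a weaker rule downstream gives up permitted rejections without buying anything. The mechanistic aim rests on a small sample: 10 evaluable and 15 enrolled, sized in section 10.1 for one paired comparison with no multiplicity adjustment. There is also an ambiguity. An analyst could read the later wording either way, and the choice should not be left until the data are seen.

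**Working it through.** **Inputs from the documents**
- Change 0.60, SD 0.6, correlation 0.50, alpha 0.05, 10 evaluable, 15 enrolled (section 10.1).
- Immune-study draws in the visit schedule: entry challenge, 8 in build-up, and Months 0, 6, 12, 18, 24 and 25. That is 1 + 8 + 6 = 15 time points.
- Markers in the flow-cytometry hypothesis of section 6.10: 9 + 4 + 2 + 5 + 5 = 25.

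**Family sizes (inferred, not stated in the plan)**
- Contrasts per marker: 15 × 14 / 2 = 105.
- Correlations, each marker counted once: 25 × 24 / 2 = 300.

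**The plan's own figure.** SD of the difference = √(0.36 + 0.36 − 2 × 0.5 × 0.36) = 0.6, so the standardised effect is 0.60/0.6 = 1.0. A two-sided paired t-test at 0.05 with n = 10 has 80.3% power. The stated 10 reproduces, but for one unadjusted comparison.

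**Thresholds**

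| Family | Bonferroni, every test | Holm, 1st | Holm, 2nd | Holm, 53rd |
|---|---|---|---|---|
| m = 105 | 0.000476 | 0.000476 | 0.05/104 = 0.000481 | 0.05/53 = 0.000943 |
| m = 300 | 0.000167 | 0.000167 | 0.05/299 = 0.0001672 | not needed |

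The first step is identical, so the probability of at least one rejection in a family is identical. Gains come only after several rejections have already been made.

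**Small illustration (invented p-values).** Take 0.004, 0.009, 0.012, 0.016, 0.024 and 0.2, so m = 6. Bonferroni's cut is 0.05/6 = 0.0083 and rejects 1. Holm's cuts are 0.0083, 0.01, 0.0125, 0.0167, 0.025 and 0.05, and it rejects 5.

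**Simulation of the contrasts.** Both rules were applied to the same p-values, using the section 10.1 inputs and 105 contrasts, without the overall-test gate. Three mean trajectories were assumed: an immediate step, a linear rise to week 50, and a step at week 24. The entries are the share of markers in which Holm adds at least one rejection; ranges run over the trajectories.

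| Error structure and test | n = 15 | n = 10 |
|---|---|---|
| Compound symmetry 0.5, model-based | 11–72% | 7–48% |
| AR(1) 0.5 per draw, model-based | 6–34% | 2–14% |
| AR(1) 0.5 per draw, paired t-tests | about 2–16% | about 0.5–3% |

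- AR(1) rescaled to give 0.5 at one year, n = 15: 8–53%.
- Size of the gain at its most favourable (compound symmetry, n = 15, week-24 step): 29.1 against 27.7 of 44 true differences. Power for baseline versus Month 0 is 66.4% against 63.0%. For the other two trajectories that contrast gains about one point.
- Error control: Holm's simulated familywise error with 105 contrasts was at most 5.0%.

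**Simulation of the correlations (300 pairs).** The true correlation of 0.85 is an assumption; the documents give none.
- n = 15, correlations clustered: 26.0 against 25.3 of 50 true correlations found.
- n = 15, all markers related: 192 against 150 of 300.
- n = 10, clustered: no gain.

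**The case against.** Bonferroni is a valid procedure at the stated level, and choosing between two valid rules for follow-up tests in a secondary aim can be called preference. That stands in part: nothing in the plan is wrong on error control. But one rule dominates the other, the plan already uses it, and no planned interval estimate needs the single-step form.

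The later wording may simply abbreviate the "step down Bonferonni correction for multiple comparisons" named just before. That is possible, since the document never says single-step. It then becomes a question of clarity, with the same remedy.

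The larger percentages are favourable cases. This stands. Section 9.2.2 starts from AR(1) and lists compound symmetry only as an alternative, and n = 15 means no attrition although section 10.1 assumes 50%. Counting markers with at least one extra rejection also hides how few extra rejections there are. The correlation result with all markers related needs a strength of association that nothing in the documents supports.

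A reader might infer that significant findings will be lost, or that this choice explains the study's low power. The documents support neither. Results can be lost, in numbers that depend on trajectory and correlation. Holm does not change the chance of a first rejection. The change from time 0 to 1 year also has its own paired t-test in section 9.2.2, although how that test is adjusted is unclear.

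**Conclusion.** The point holds as a matter of efficiency and consistency. Naming Bonferroni for the contrasts and correlations, read literally, gives up rejections that the same familywise guarantee allows.

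The loss is never negative. For the contrasts it runs from negligible (AR(1) 0.5 with paired t-tests, n = 10) to material (compound symmetry, n = 15, mid-build-up step). For clustered correlations at n = 10 it is nil, and it is large only if many true correlations are strong.

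These sizes rest on inferred families of 105 and 300, on assumed trajectories and correlation strengths, and on an error structure that the plan leaves to Akaike's criterion. The existence of the gain rests on none of them. It is a free improvement, not an error in type I control and not a remedy for small numbers.

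**What to change.** In section 9.2.2, name Holm's step-down procedure in the sentence on pairwise time comparisons and in the sentence on Spearman correlations. In the same edit, state what each family contains: which time points, which markers and which cell types. The cost is a few words and one software option. No further assumption is needed, and the familywise level stays at 0.05. Make the change before the immune data are analysed.

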10. STATISTICAL CONSIDERATIONS

10.1. *Sample size considerations:*

Sample size was estimated to detect a statistically significant difference in the proportion of T cells producing interferon-gamma (IFN gamma), at the 1 year time point compared with baseline using a paired t-test. A difference in proportions of 0.60 units (.2 at baseline and .8 at 1 year) would be clinically important. Assuming a common SD=0.6 at each time point, correlation between repeated measures is 0.50 and alpha = 0.05, a sample size of 10 subjects would be required to detect this difference with 80% power. Assuming 50% attrition, this study will plan to enroll a total of 15 subjects.

Notes:

- 13 subjects for 90% power with alpha=0.01
- 16 subjects for 80% power with alpha=0.01
- 19 subjects for 90% power with alpha=0.01

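### The marker-to-marker partial correlations in 9.2.2 remove child but not visit, so two unrelated markers that both shift substantially on similar time courses during OIT will correlate through the shared treatment trend

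*Combined protocol and SAP*

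**What the plan says.** Section 9.2.2 plans two analyses of association between activation responses.

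- Rank correlations: "Spearman rank correlations will be estimated for all pairwise comparisons between activation responses". It then adds: "P-values for testing for significant correlations will be adjusted using Bonferonni's correction for multiple comparisons". It does not say which visits enter or how repeated visits from one child are handled.
- Partial correlations: "Partial correlation coefficients will also be estimated for all activation responses adjusting for subject-level effects across all time points". The only adjustment named is for subject. This sentence comes after the p-value sentence and speaks only of estimation.

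The same section has a general linear mixed model with time as a discrete fixed effect and a first-order autoregressive error structure as the starting choice. That model is for change in each response over time. Nothing carries its time effect into the correlations.

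The hypothesis in Section 6.10 (Scientific Rationale for Immune Cell Response Studies) expects several markers to be higher after desensitization: T-bet, IL-5, IL-10, IFN-gamma and IL-17, together with "FOXP3 expression and an increased regulatory and memory T cell phenotype".

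**The concern.** Centring each child's values removes stable differences between children. It does not remove a mean time course that all children share. If two markers both move over the course of OIT, the centred values of both carry that movement, and their correlation contains it even when, at a given visit, a child who is high on one marker is no more likely to be high on the other.

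The protocol expects several markers to shift, so the condition for this is part of its own hypothesis. The mixed model already tests whether each marker changed. The correlations are useful for what they add to that, namely whether T helper, regulatory and iNKT responses are linked. A child-only coefficient mixes the two questions, and a reader could take a shared response to treatment for coordinated regulation.

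**Working it through.** **The plan's own figure.** Section 10.1 gives the planning inputs: "A difference in proportions of 0.60 units (.2 at baseline and .8 at 1 year) would be clinically important", and "Assuming a common SD=0.6 at each time point, correlation between repeated measures is 0.50 and alpha = 0.05". The SD of the paired difference is 0.6 × √(2 × (1 − 0.5)) = 0.6, so the standardised effect is 0.60/0.6 = 1.0. An exact two-sided paired t-test with n = 10 has power 0.803, which reproduces the stated 10 subjects at 80%. The documents give no figure for the correlation analysis, so these inputs are borrowed for it.

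**Inputs for the check**
- Within-child variance: 0.36 × (1 − 0.5) = 0.18. Between-child variance: 0.18.
- Draws (schedule table, Section 6.12): entry challenge, eight in build-up, Month 0 challenge, and months 6, 12, 18, 24 and 25, which makes 15. Taken as weeks 0 to 48 by 6, then 54, 80, 106, 132, 158 and 162.
- Assumption: the mean rises linearly to week 52 and is then flat.
- Assumption: the two markers are independent given child and visit, with independent errors over time.
- Children: 15 enrolled, 10 as the planned evaluable number, and 7 as roughly half of 15 (the stated 50% attrition).
- Pairs: Section 6.10 lists 9 + 4 + 2 + 5 + 5 = 25 markers, so 25 × 24/2 = 300 if each is counted once. The Bonferroni level is 0.05/300 = 0.00017.

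**Expected child-only coefficient.** For two markers with the same shift, r = V/(V + 0.18), where V is the variance of the visit means (divisor: visits minus 1).
- The ramp values are week/52 up to week 48, then 1 for the last six draws. Their mean is (216/52 + 6)/15 = 0.677. Their sum of squares about the mean is 7344/2704 + 6 − 15 × 0.677² = 1.84, and 1.84/14 = 0.132.
- Shift 0.60 (1 SD): V = 0.36 × 0.132 = 0.047, r = 0.047/0.227 = 0.21.
- Shift 0.30 (0.5 SD): V = 0.09 × 0.132 = 0.012, r = 0.06.
- Shift 0.15 (0.25 SD): V = 0.0225 × 0.132 = 0.003, r = 0.02.
- At 1 SD with only the 10 draws to Month 0: r = 0.19. With only baseline and one year: V = 0.36 × 0.5 = 0.18, r = 0.50.
- Opposite shifts of 1 SD: r = −0.21. Only one marker shifts: r = 0. A ramp against a transient rise in mid build-up: r = −0.09 (15 draws) or −0.03 (10 draws).

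**Rejection rates if a t test were applied** (simulation, 2,000 runs per scenario, unrelated markers, child-only adjustment, 15 draws):

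| Children | 1 SD, at 0.05 | 1 SD, at 0.05/300 | 0.5 SD, at 0.05 |
|---|---|---|---|
| 7 | 56% | 4% | 9% |
| 10 | 69% | 8% | 10% |
| 15 | 86% | 23% | 15% |

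Repeat simulations agree to within a few points, hence the rounded range of 55% to 87% at 1 SD.

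**Child and visit both removed.** The mean coefficient is about 0 (−0.01 to 0.01) in every scenario, and rejection at 0.05 is 3% to 7%. This holds for independent errors. With within-child AR(1) of 0.5, the ordinary t test still rejects about 11% to 12%, while permuting whole-child series gives about 4%.

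**Spearman.** If all visits were pooled as though independent, two unrelated markers with no shift at all would be declared correlated about 34% of the time with 15 children, because each child's own level repeats across visits.

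**The case against.** Several points on the other side stand.

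- A reader might infer that any two markers that shift will appear linked. The figures do not support that. At 0.25 SD there is no visible inflation, at 0.5 SD the coefficient is 0.06, and dissimilar time courses give little.
- The 1 SD shift is planned for IFN-gamma alone. Nothing applies it to the other markers, and Section 9.2.2 analyses log-transformed data, so the ratio 0.60/0.6 need not carry over.
- Fifteen draws is near the maximum. Section 6.4 says that build-up length depends on the starting dose. On Table 3's two-week steps, a child starting at 750 mg (dose 15 of 26) needs 11 steps, about 22 weeks, and so has fewer build-up draws.
- The partial correlations are only to be estimated. The rejection rates describe a test that the plan does not state, and if the Bonferroni rule were meant to cover them, most null pairs would not be declared significant.
- A child-only coefficient legitimately describes how two markers move together during OIT, and the aim is framed as responses before and after desensitization. Removing visit answers a different question.
- A reader might infer that the Spearman analysis pools visits. The text does not say so. This is a missing specification, not a demonstrated error.

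These points limit the size and reach of the problem but do not remove it. The coefficient carries the shared trend whether or not it is tested, and the plan does not label it as co-movement. Bonferroni is also less protective under the plan's own AR(1) structure: at a correlation of 0.5 and a 1 SD shift, rejection at 0.05/300 rises to about 22% with 10 children and 38% with 15.

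**Conclusion.** The concern holds for pairs of markers that both shift substantially on similar time courses. For these, the child-only partial correlation partly or wholly restates the common treatment response. The bias is material at the plan's own IFN-gamma effect, small at half that effect, and absent when only one marker moves. The figures rest on the assumed ramp and plateau, complete draws, independent errors and equal shifts in the two markers. The finding concerns a secondary mechanistic analysis and has no bearing on safety or on the primary objective. It is worth correcting because the remedy is simple and uses models that are already planned.

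**What to change.** In Section 9.2.2:

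1. Also estimate the partial correlations after removing both child and visit, for example from residuals of the planned mixed models with discrete time. Use these for any statement that markers are linked beyond the common treatment response.
2. Keep the child-only coefficients if wanted, labelled as descriptive co-movement during OIT.
3. State whether the partial correlations are tested and whether the Bonferroni rule covers them. If p-values are given, obtain them by permuting whole-child series.
4. Compute Spearman correlations within a visit (baseline, one year) or on each child's change from baseline to one year, and say which.

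No new data, visits or patients are needed. The cost is a second set of coefficients and a permutation step. That step has a limit in small samples: with 7 children there are 7! = 5,040 arrangements, so the smallest p-value is 1/5,040 = 0.0002, just above 0.05/300 = 0.00017. Eight children (40,320 arrangements) clear it.

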The process of desensitization through immunotherapy occurs after an initial food challenge to determine what amount of food allergen causes a clinical reaction in the subject. There are two phases in treatment with oral immunotherapy. In the first phase, the build-up phase, the subject ingests gradually escalating doses of peanut flour, administered orally in a vehicle once every day with weekly or bi-weekly dose escalation. Once a maintenance dose has been achieved, the subject continues to take this amount in a peanut equivalent dose over a period of years. Peanut equivalent dosing has been used in several prior peanut OIT trials without report of increased side effects or adverse events. (17-20) The peanut flour manufacturer for the initial trials in peanut oral immunotherapy by centers in the Consortium of Food Allergy Research (CoFAR) only provided dosing for the buildup phase for the trials and peanut equivalent dosing was used by centers for the maintenance phase. (Personal communication) Therefore, given the experience with peanut equivalent dosing, after the first year of this study, patients will be switched to a daily peanut equivalent dose and intake will be monitored by daily diaries. Since the daily dose will still be 3900 mg of peanut protein for the maintenance phase, the immunologic effects of the peanut dosing are not likely to be affected. (11, 12)

An open label study with an initial dose of 100 µg increased to 300 mg maintenance dose for several months demonstrated efficacy in over 90% of the subjects with desensitization and tolerance of a 3900 mg dose on food challenge.(11,12) A follow up double blind study

demonstrated efficacy with treated subjects tolerating 5000 mg compared to 280 mg in placebo subjects. The safety analysis of these studies demonstrated that 93% of children experienced symptoms on initial dosing day with 15% requiring epinephrine.(9) Most reactions were mild. However, when the initial dose was decreased from 50 mg down to 6 mg, allergic side effects were noted in only 47%. Of 10,184 home maintenance dosings of peanut flour, only 3.5% caused symptoms, with 2 subjects receiving epinephrine, each after one maintenance dose (0.02%). The relative safety of this approach has been demonstrated in these initial trials.(9)

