2. OBJECTIVES

2.1 *Primary Objectives:*

- 2.1.1. The primary objective is to determine whether peanut oral immunotherapy safely develops clinical tolerance in peanut allergic patients by assessing the change of dose tolerated and to determine the percentage of subjects who can tolerate 6 g of peanut flour with absence of clinical symptoms during a food challenge following the initial desensitization phase of peanut flour which includes a 50 week dose escalation phase and 104 week maintenance phase on a peanut equivalent dose.

2.1. Secondary Objectives:

To determine the immune mechanisms of clinical tolerance, using technology to identify T cell cytokine responses and subsets, as well as basophil activation responses as measured by flow cytometry. T and NKT cell function and intracellular cytokine expression will be measured.

2.2.1. To determine whether viral exposure potentiates response to in vitro peanut allergen exposure and to assess those changes during peanut OIT.

2.2.2. To compare the change in dose tolerated after one month of abstaining from peanut to determine sustained unresponsiveness.

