Cytokine production of T lymphocytes has been performed in peanut allergic patients but this is typically performed through multiplex ELISA from supernatants of cultured cells. (43-46) Intracellular cytokine staining of T cells has been performed in peanut allergic patients (32, 46-47) but the relationship of production of T cell cytokines and transcription factors intracellularly in peanut allergy has not been studied.

In prior investigations of intracellular T cell responses in peanut allergic disease, the number of cytokines assessed was no more than four or five per cell. The cytokines assessed have included IFN- γ , TNF- α , IL-4, IL-5, IL-10 and IL-17. Makedonas et al. (16) have established a model of assessment of T cell activation through a polyfunctional 14 color flow cytometry in virus specific CD8+ T cells. (16) Intracellular cell surface markers, cytokines and transcription factors were analyzed with this approach. This comprehensive examination of T lymphocyte function has never been performed in the context of food allergic disease. We propose to evaluate peanut specific CD4+ T cell activation by polyfunctional analysis in distinct clinical phenotypes of peanut allergy. The ability to determine TH1, TH2, TH17 iNKT and T regulatory responses on a cellular level will give further insight into the mechanisms controlling the clinical expression of food allergy.

6.8. Correlative studies:

The peanut-specific immunoglobulin G and G4 tests and immune cell experiments in this study are designed for research, not for medical purposes. They are not useful for finding problems or diseases. Even though the researchers are not looking at the subject's peanut-specific immunoglobulin G and G4 tests to find or treat a medical problem, he or she will be told if they notice something unusual. The subject and his or her regular doctor can decide together whether to follow up with more tests or treatment. Because the food-specific immunoglobulin G and G4 tests and immune cell experiments done in this study are not for medical purposes, the research results will not be sent to the subject or to their regular doctor.

The basophil histamine release assay, also known as the basophil activation test (BAT) will be performed on blood samples collected from subjects throughout the study. The findings from BAT are designed for research and will not be sent to the subject or their regular doctor.

6.9. Procedures for storing of extra or left over samples:

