8. DATA MANAGEMENT ISSUES

8.1. Sources of Research Material:

8.1.1. Existing records:

Previous CAP-FEIA serum IgE reports will be included in each subject's record. Existing subject medical records will not otherwise be used unless records are needed to verify or clarify the severity of the original reaction to peanut ingestion.

8.1.2. Data collected during research:

- Consent and assent
- Demographic information (age, sex, ethnicity)
- History and Physical examination (including diet history, family history, past medical and past surgical history)
- Allergy skin prick testing to peanut
- Mechanistic blood draws
- Serum Beta HCG and urine pregnancy test for all menstruating females.
- Observed dosing adverse event log.
- Concomitant medication administration while on study.
- Spirometry and/or peak flow
- Double-Blinded Placebo Controlled Food Challenge (DBPCFC) (for those with confirmed CAP-FEIA serum IgE > 7 and a negative pregnancy test).

8.1.3. Home diaries:

Symptom diaries will be recorded daily by participants.

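### Objective 2.2.1 asks an in vitro question, but its analysis in 9.2.3 counts symptomatic doses only and cannot show whether viral symptoms raise reaction risk

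*Combined protocol and SAP*

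**What the plan says.** Section 2 (Objectives), item 2.2.1, states the aim: "To determine whether viral exposure potentiates response to in vitro peanut allergen exposure and to assess those changes during peanut OIT".

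Section 9.2.3 gives the analysis for the second secondary objective. It records "the number of episodes of prior viral infection symptoms experienced after symptomatic daily peanut dosing", and then: "This number will be compared to the episodes of symptomatic daily peanut dosing with no prior viral infection symptoms". It adds exact binomial intervals for a proportion of subjects, and continues: "This analysis will also be used to determine the proportion of symptomatic daily doses with preceding symptoms of viral infection", set against symptomatic doses not associated with viral symptoms.

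Section 9.2.3 belongs to 2.2.1. Section 9.2.2 analyses the flow cytometry objective, and 9.2.4 compares the 24 and 25 month challenges, which is objective 2.2.2.

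On data collection, section 8.1.3 says: "Symptom diaries will be recorded daily by participants". Appendix III asks families to record symptoms within 2 hours of the dose. Appendix VIII asks for daily completion, with symptoms in the observation period.

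**The concern.** There are three faults.

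- **The question and the analysis differ.** The objective concerns a laboratory response and the analysis counts clinical episodes.
- **A denominator is missing.** Taken clinically, both counts in 9.2.3 and the final proportion are restricted to doses that caused symptoms. Whether viral symptoms raise risk depends on how often symptoms follow a dose with and without preceding viral symptoms. That comparison needs the symptom-free doses.
- **The time order is unclear.** Viral symptoms are called *prior* yet counted as occurring *after* the symptomatic dose, and no look-back window is set. Two analysts could obtain different counts from the same diaries.

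*Potentiates* is a claim about an effect. If the plan is followed as written, that claim is untested in the laboratory and cannot be assessed clinically. Section 9.1 also sends responses on the secondary objectives to the monitoring committee every 6 months, so a share with no clear interpretation would be reviewed repeatedly.

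**Working it through.** The plan gives no rate, effect size or power for this objective, so there is no planning figure to reproduce. The check has two parts.

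**Is there an in vitro viral comparison elsewhere?** The section on the scientific rationale for immune cell response studies describes peanut-specific T cell, NKT cell and basophil work with no viral condition. Its only mention of a virus is in earlier work that supplied the method: "assessment of T cell activation through a polyfunctional 14 color flow cytometry in virus specific CD8+ T cells". The mixed model in 9.2.2 names time as its only fixed effect. Neither supplies the comparison.

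**What can the clinical share identify?** Let *s* be the viral share among symptomatic doses (what 9.2.3 estimates) and *q* the share of all doses preceded by viral symptoms (what it does not). The relative risk of a symptomatic dose, with versus without preceding viral symptoms, is

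RR = s(1 − q) / [q(1 − s)].

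Inputs:
- Section 1: "Of 10,184 home maintenance dosings of peanut flour, only 3.5% caused symptoms". Then 0.035 × 10,184 ≈ 356 symptomatic doses, and 10,184 − 356 = 9,828 symptom-free doses (96.5%), none of which enters 9.2.3.
- *s* = 30%, assumed: 107 viral and 249 non-viral symptomatic doses.
- *q* from 10% to 50%, assumed. The documents give no value.

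| q | Risk with viral symptoms | Risk without | RR |
|---|---|---|---|
| 10% | 107/1,018 = 10.5% | 249/9,166 = 2.7% | 3.9 |
| 20% | 107/2,037 = 5.2% | 249/8,147 = 3.1% | 1.7 |
| 30% | 107/3,055 = 3.5% | 249/7,129 = 3.5% | 1.0 |
| 50% | 107/5,092 = 2.1% | 249/5,092 = 4.9% | 0.43 |

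Section 9.2.3 would report the same 107 against 249 in every row. The pattern does not hinge on 30%: a share of 25% (89 of 356) gives RR 6.3, 3.0, 1.0 and 0.5 at *q* = 5%, 10%, 25% and 40%. An exact 95% interval for 89/356 is 20.6% to 29.8%. It describes the share only, and it treats repeated doses from one child as independent.

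**Would an all-dose analysis work at this size?** An illustrative simulation used 600 runs per scenario with 8, 12 or 15 children and 1,000 doses each. Apart from the 3.5% base rate its inputs are assumed: between-child SD 0.8 on the logit scale, child-specific viral frequency, 7-day illnesses, a build-up odds ratio of 1.5, and no further serial correlation. The model was a logistic GEE clustered by child and adjusted for phase, with Mancl–DeRouen standard errors and a t reference with (children − 1) degrees of freedom.
- Median estimates for true odds ratios of 3.86, 2.0, 1.0 and 0.43 were 3.5–3.6, 1.9, 0.98–1.01 and 0.44–0.45.
- Nominal 95% intervals covered 93–97% of the time, against 62–86% when child was ignored.
- At a true odds ratio of 2 and *q* = 10%, the central 95% of estimates was 1.34–2.72 with 15 children, 1.27–2.66 with 12 and 1.14–2.93 with 8.

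**The case against.** The strongest reply is that 9.2.3 is descriptive: it counts, estimates a proportion and names no test. In a single-arm study of 15 children sized on interferon-gamma, an effect model may seem more than is needed. The share is indeed a valid description. It is, however, the only analysis assigned to an objective worded as an effect.

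The share is also not wholly uninformative. RR exceeds 1 whenever *s* exceeds *q*, so a share of 80% would point to harm unless viral symptoms preceded more than 80% of doses. That stands. The conclusion is therefore that the effect is not identified without outside knowledge of *q*. The ambiguity between harm and protection bites for mid-range shares.

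The reviewed text is incomplete. A figure after 9.2.4 is not shown and most of the diary form is missing. A surviving diary line invites comments on symptoms unlikely to be due to the dose, so some viral symptoms on symptom-free days may be captured. The denominator for the proportion of subjects is unstated and might include children who never react. None of this brings symptom-free doses into the comparison that 9.2.3 describes.

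Finally, the all-dose model has its own weakness. Upper-respiratory signs are both viral symptoms and Grade 1 reaction signs (section 12.4, Table 8). With no true effect and a 3.5% base risk, wrongly counting such a sign on a fraction *x* of viral days gives a risk of 0.035 + 0.965*x*. For *x* = 2% this is 5.4% (odds ratio 1.6), and for *x* = 5% it is 8.3% (odds ratio 2.5). The simulation spread at 15 children implies a log-scale standard error near ln(2.72/1.34)/3.92 = 0.18, so these biases are about 2.5 and 5 standard errors. The simulation included no such misclassification. This stands as a limit on interpretation. The planned share has the same problem, so it is no reason to keep the share alone.

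**Conclusion.** The concern holds. The mismatch between 2.2.1 and 9.2.3, and the contradictory time order, can be read directly from the text. The missing denominator follows from the algebra and not from any chosen value: one and the same reported share can fit relative risks from 3.9 to 0.43 over the range of *q* shown. More children or a narrower interval would not cure it. The 30% share and all values of *q* are assumptions, and the 3.5% rate is the protocol's background figure for home maintenance doses in earlier studies. The consequence is confined to one secondary objective. The primary, safety and sample-size conclusions are untouched. It should be corrected, preferably while viral status on symptom-free days can still be recorded.

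**What to change.** - Reword 2.2.1 as the clinical question that 9.2.3 addresses. If the sponsor wants to keep the in vitro question, it must define an assay with a viral-exposure condition and its analysis, which the protocol does not now describe.
- In 9.2.3, take all diary dose days as the denominator. Classify each by preceding viral symptoms (yes/no) in a look-back window fixed before analysis, for example 7 days. Replace the prior/after wording with *preceding*.
- Compare the probability of a symptomatic dose with and without preceding viral symptoms in one logistic GEE clustered by child, with small-sample-corrected standard errors, adjusted for phase (build-up or maintenance).
- Report the odds ratio with its interval as an association, stating the overlap with Grade 1 signs. Keep the viral share as a description. Any dose-level interval should allow for repeated doses within a child.

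**Cost:** wording changes and one model. If the diary has no suitable item, add one yes/no entry per dosing day: about 350 days (50 weeks) plus 730 days (24 months) = 1,080 per child, or at most 15 × 1,080 = 16,200, plus data entry for symptom-free days. Days before the change must be treated as missing, not as free of viral symptoms. The interval may be wide, especially with about 8 children, which is roughly what the assumed 50% attrition would leave of 15.
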